#### Research questions and hypotheses

Primary research question:

What are the main factors associated with increased risk of PRMDs in music students undertaking professional training?

Secondary research questions/objectives:

- 1. What is the prevalence of musculoskeletal disorders among university-level students in comparison with pre-college students?
- 2. Monitor and characterise the impact of the transition between pre-college and university-level music training on the development of PRMDs.
- 3. (Are there any differences in the severity and symptoms associated with PRMDs among music student groups at different levels of music training?)
- 4. Monitor and characterise the time course of PRMD development

- 5. (Are there significant differences in PRMD incidence between university-level students and pre-college students?
- 6. During training, do music students develop any type of musculoskeletal disorder that doesn't affect their ability to play at the level to which they are accustomed to?
- 7. Characterise health related quality of life and outcomes in music students at different stages of professional training.

Considering the aims and the research questions of the programme, the following hypotheses are formulated:

H1: The development of PRMDs is associated with a multitude of risk factors (i.e. age, gender, number of hours of practice, previous history of injury, poor physical status, psychological stress, perfectionism, fatigue) among music students.

H2: There is a higher prevalence of PRMDs among university-level students in comparison with precollege students.

H3: There is a higher prevalence of PRMDs among university-level students in the early stages of their training (transition between university-level and pre-college).

H4: University-level students develop more PRMDs over the years of their training than pre-college students.

H5: During their training, music students of both levels develop MSK disorders that affect their ability to play at the level they are accustomed to.

H6: Health and quality of life among music students is progressively poorer over the years of training (from the last two years of pre-college to the last years of Master-level)

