# The web-based survey

The web-based survey will include different outcome measures, which have been selected according to the relevant findings of previous cross-sectional studies and systematic reviews among the performing arts literature (Figure 2).

Each outcome measure correspond to a suspected factor that may be associated with the development of PRMDs.

The survey will start with questions about personal background and lifestyle (i.e. age, gender, self-reported weight and height, nationality, smoking status and sleeping habits), as well as practice habits (i.e. number of

hours of practice and years of experience) health history (i.e. major past injuries/accident/disorders and current medication) and health status (Self-Related Health - SRH).

Afterwards, in order to divide the cohorts, the presence of pain and/or MSK problems will be assessed through the following question: "When did you last experience a bout of significant pain and/or musculoskeletal problem?" with the following list of possible answers:

- 1. I currently have pain and/or a musculoskeletal problem (up to one month)
- 2. 2-3 months ago
- 3. 4-6 months ago
- 4. Up to 12 months ago
- 5. More than 12 months ago
- 6. I have never had any pain and/or musculoskeletal problem

[figure not shown]

Figure 2 Procedure of the web-based survey

According to the answer to this question, students will be addressed to different web pages throughout the survey (Figure 2):

- Respondents with a current pain and/or MSK problem (up to one month) will be asked questions to describe their current pain, to report their disability with Pain Disability Index (PDI), the Performing Arts

Section of Quick Disabilities of the Arm, Shoulder and Hand Outcome Measure (PAS –Quick DASH) and their pain self-efficacy with 2-item short form of the Pain Self-efficacy Questionnaire (PSEQ-2), as well as the Nordic Musculoskeletal Questionnaire (NMQ) for the assessment of musculoskeletal pain in the last 12 months

- Respondents without a current pain and/or MSK problem but a positive history of pain and/or MSK problem in the last 12 months (2-3 months ago, 4-6 months ago or up to 12 months ago) will be asked to answer the NMQ and questions on pain management to investigate how their pain and/or MSK problem has been treated
- Respondents without pain or with pain and/or MSK more than 12 months ago will be directly addressed to the next section

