All respondents will be addressed to the next section, including the outcome measures:

International Physical Activity Questionnaire – short form (IPAQ-SF) for the assessment of physical status Kessler Psychological Distress Scale (K-10) for the assessment of anxiety and stress

Multidimensional Perfectionism Scale – short form (HFMPS-SF) for the assessment of perfectionism

The Chalder Fatigue Scale (CFQ-11) for the assessment of fatigue

Afterwards, all students (including those who will choose the sixth option) will be addressed to:

- International Physical Activity Questionnaire short form (IPAQ-SF) for the assessment of physical status
- Kessler Psychological Distress Scale (K-10) for the assessment of anxiety and stress
- Multidimensional Perfectionism Scale short form (HFMPS-SF) for the assessment of perfectionism
- The Chalder Fatigue Scale (CFQ-11) for the assessment of fatigue

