#### Data analysis

Descriptive statistics will be used to investigate all the outcomes after the baseline data collection.

Furthermore, comparisons of gender, study, prevalence rate and hours of practice between pre-college and university-level students of music will be performed.

Baseline variables will be categorized to permit the calculation of risk ratios and the 95% confidence intervals (CI) for the development of PRMDs. Tests for trend of relative risk across categories will be carried out using the chi-square test. In order to check for confounders, logistic regression will be performed, adjusting for age, gender and different musical instrument.

Sample size estimation is reported in Figure 1.

Both the follow-ups will permit longitudinal change in outcome scores to be generated and compared (longitudinal comparisons) for strength and progression of association, alongside those from absolute outcome scores at several cross-sectional analyses.

For the evaluation of the association between the variables (gender, instrument group, age, years of playing, hours of practice, and questionnaires' scores) and pain, PRMD and/or MSK problem incidence, univariate analysis will be performed. Afterwards, all predictor variables that are significantly associated with the

occurrence of PRMDs will be included in a multivariate regression model to estimate the mutually adjusted effect of predictors on PRMDs.

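### Risk factors are picked by univariate significance and then estimated on the same students, so the adjusted model's confidence intervals and p-values ignore the selection

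*Protocol*

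**What the plan says.** H1 (Protocol, Research questions and hypotheses) reads "The development of PRMDs is associated with a multitude of risk factors" and gives eight examples: age, gender, hours of practice, previous injury, physical status, psychological stress, perfectionism and fatigue. It does not say how many associations would support it.

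The Data analysis section offers two routes.

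- **Risk ratios.** "Baseline variables will be categorized to permit the calculation of risk ratios and the 95% confidence intervals (CI) for the development of PRMDs". A logistic regression adjusting for age, gender and instrument then checks for confounding.
- **Screen and refit.** The candidates are "gender, instrument group, age, years of playing, hours of practice, and questionnaires' scores". For "questionnaires' scores) and pain, PRMD and/or MSK problem incidence, univariate analysis will be performed". Variables that prove significant there move to a second step, described as follows: "occurrence of PRMDs will be included in a multivariate regression model to estimate the mutually adjusted effect of predictors on PRMDs".

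The univariate analyses cover the wider composite of pain, PRMD and musculoskeletal problems, but the entry sentence refers to PRMDs. The section states no significance level for entry, holds back no data, and plans no validation or shrinkage. It does not call the screened model exploratory. Under Study Design, the primary question is to be answered from the follow-up of Cohort 1, the students free of problems at baseline.

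**The concern.** The second model is the only one in the plan that adjusts the candidate factors for each other, so a reader will take it as the answer to the primary question. Its usual standard errors assume that its terms were fixed before the outcome was seen. Here a variable is present because it was already significant in the same students. Significance in the second step is then largely a repeat of the first, yet it reads as confirmation after adjustment.

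Two things follow. Some variables with no association will enter and stay. For those that enter, the estimates tend to be too large, because a variable is kept only when its estimate falls far enough from the null.

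This matters for use. The Background section wants modifiable factors to guide targeted behaviour change and health promotion, and it faults earlier work for inappropriate statistical analysis. A chance factor with a tidy adjusted interval could misdirect that effort.

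**Working it through.** The plan states no significance level, familywise error or power, and its sample size is in a figure not shown. There is no stated figure to reproduce. The chance of a false factor in the independent case does not depend on the sample size.

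**Number of candidates**

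- Data analysis names five variables: gender, instrument group, age, years of playing and hours of practice.
- It adds questionnaire scores. The web-based survey section says "Afterwards, all students (including those who will choose the sixth option) will be addressed to" four scales: IPAQ-SF, K-10, HFMPS-SF and CFQ-11. With one total score each (assumed), 5 + 4 = 9.
- Self-rated health, also asked of everyone, makes 10.
- If every baseline item were screened, the survey's background list ("age, gender, self-reported weight and height, nationality, smoking status and sleeping habits") adds weight/height as one item, nationality, smoking and sleep. Past injuries and medication add two more. That is 6, so 10 + 6 = 16.

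**Level per test.** 5% two-sided is assumed. The nearest support is the 95% CI for the risk ratios.

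**Screen, no true associations, independent tests.** P(at least one false factor) = 1 − 0.95^k:

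| k | at least one | two or more |
|---|---|---|
| 9 | 37.0% | 7.1% |
| 10 | 40.1% | 8.6% |
| 13 | 48.7% | 13.5% |
| 14 | 51.2% | 15.3% |
| 16 | 56.0% | 18.9% |

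**Screen with equally correlated test statistics** (200,000 simulated runs), at least one false factor:

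| correlation | k = 10 | k = 16 |
|---|---|---|
| 0.2 | 37.7% | 51.8% |
| 0.3 | 35.2% | 47.5% |
| 0.5 | 28.7% | 37.5% |

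**Screen followed by refit on the same data** (4,000 runs; assumed n = 300 and 30% incidence; linear approximation). The table shows studies with at least one false factor:

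| correlation, k | after screen | still significant after refit | share remaining |
|---|---|---|---|
| 0, k = 10 | 39.2% | 38.9% | 38.9/39.2 = 99% |
| 0, k = 16 | 56.9% | 56.4% | 56.4/56.9 = 99% |
| 0.3, k = 10 | 35.5% | 29.6% | 29.6/35.5 = 83% |
| 0.3, k = 16 | 47.2% | 35.1% | 35.1/47.2 = 74% |

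**Why the intervals fail.** At 5%, a variable enters only if its univariate estimate lies more than about 1.96 standard errors from the null. Every null variable that enters therefore has a univariate 95% CI that excludes the true value. With independent predictors the refit hardly moves that estimate, so its interval almost always misses the truth as well. The same cut-off discards small estimates and keeps large ones, which biases the retained estimates away from the null.

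**The case against.** Several points on the other side are sound and limit the claim.

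- **Size.** A reader might infer that chance yields a risk factor in more than half of studies. That needs at least 14 independent tests at 5%, and the screening list gives 9 to 10. Distress, fatigue and perfectionism are plausibly correlated, as are age and years of playing, which lowers the figure. The count of 16 uses baseline items from the risk-ratio step, and nothing says these feed the screened model.
- **Outcomes and visits.** It is tempting to multiply the tests across two outcomes and two follow-ups, which gives much higher rates. But entry is tied to the occurrence of PRMDs. No sentence admits a variable that passes on any outcome at any visit.
- **H1.** It is also tempting to say that H1 counts as supported once any variable passes. The Protocol does not say so, and one chance factor is not a multitude. Two or more arise by chance in about 9% with 10 independent tests. What holds is that H1 has no stated decision rule.
- **Other routes.** The risk ratios, and the logistic regression with a fixed adjustment set, do not depend on the screen.
- **Purpose.** The aim is to identify associated factors. Strict familywise control is debatable in an observational risk-factor study, and an alpha or multiplicity rule could sit in an analysis plan that is not shown.

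These points do not remove the core problem. The entry rule is written into the Protocol, so it is not a detail deferred to a later plan. Choosing terms by significance and then reporting ordinary intervals from the same data is unsound whether or not one controls familywise error.

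**Conclusion.** The concern holds in limited form. The plan selects predictors by univariate significance and presents their adjusted effects from the same students as if the model had been fixed beforehand.

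Per analysis, with no true associations and an assumed 5% level, at least one false factor is expected in about 37-40% of studies for the 9 to 10 listed variables if independent. The range for 10 variables at correlations of 0.3 to 0.5 is about 29-35%, and the figure for 16 independent variables would be about 56%. The refit removes almost none of these under independence and some under correlation. The more general fault does not depend on all associations being absent: the final CIs and p-values take no account of selection, and retained estimates are exaggerated.

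The documents do not support saying that most such studies would produce a false factor, that one passing variable settles H1, or that the refit never helps. This is a change the sponsor should make; it does not invalidate the whole study.

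**What to change.** In Data analysis, replace the univariate entry rule with wording to this effect:

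- The primary analysis is one multivariable model, fixed before follow-up outcomes are examined, for PRMD by 12 months in Cohort 1.
- It contains baseline values of the eight H1 factors plus instrument group and years of playing, 8 + 2 = 10 factors. All are kept whatever their univariate p-value. Previous injury is an H1 factor that the present screening list does not name, so this also closes that gap.
- The primary answer is read from that model's estimates and 95% CIs, and the report states how many factors were examined.
- Univariate results, the 6-month and composite outcomes, change-score analyses and any model with data-selected terms are labelled exploratory and are not offered as confirmation of H1.

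Multiplicity-adjusted p-values such as Holm may be shown alongside as an option. A single global test is not a substitute: it can reject because of one factor, so it cannot show a multitude.

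The cost is analysis wording only, with no new data or participants. CIs will be somewhat wider because all variables stay in, and fewer factors may be named. Instrument group may need several parameters, so the model's size should be checked against the expected number of PRMD cases. The text available here does not allow that check.

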Files deposited in the Research Collection will be given a Digital Object Identifier (DOI). The retention schedule for data will be set to 4 years from date of deposition in the first instance, with possible extension for datasets which remain in regular use.

The DOI issued to datasets in the repository can be included as part of a data citation in publications, allowing the datasets underpinning a publication to be identified and accessed.

Metadata about datasets held in the Research Collection will be publicly searchable and discoverable and will indicate how and on what terms the dataset can be accessed.

#### **Ethical considerations**

The study will be carried out using self-reported evaluations and will involve human beings. Furthermore, anonymity of the participants will be guaranteed when collecting information, analysing or publishing in scientific journals. Individual participant's information obtained as a result of this research project will be considered confidential and disclosure to third parties will be prohibited. Participant's confidentiality will be further ensured by utilising identification code numbers to correspond to participants' information in the Surveymonkey® software and the computer files. All participants will be informed that the participation in the study is voluntary and that they may withdraw from the study at any time.

An electronic consent of a participant will be obtained before the participant is submitted to any study procedure. If a medical condition is discovered or suspected, respondents will be suggested to visit a medical doctor. Moreover, at the end of the questionnaire all respondents will be provided with detailed information about all local medical doctors, physiotherapists and clinics, as well as research initiatives, and providers of medical support.

#### **Resources and costs**

Item	Quantity	Cost/Unit (£)	Cost (£)
Equipment/consumables			
Surveymonkey tool Incentives for participating in the study (i.e.	2	367	734
Amazon gift cards)	4	50	200
Subtotal			934
Travel			
Conference attendance			4'000
Subtotal			4'000

# Total 4'934

# Project time plan

The project has three interrelated work packages (WP):

WP 1: Data collection

		Year 1				Year 2				
Activity	Milestones	T1	T2	Т3	T4	T1	T2	T3	T4	
Data collection	Participants' recruitment									
	First data collection (baseline)									
	1st follow-up									
	2nd follow-up									

WP 2: Data analysis and interpretation of the findings

		Year	1			Year 2			
Activity	Milestones	T1	T2	Т3	T4	T1	T2	T3	T4
	Cross-sectional baseline analysis								
Data analysis and interpretation	Preliminary analysis of the results								
	Analysis of the results								
	Assessing and discussing the findings								
of the findings	Individuating possible trends								

WP 3: Dissemination

		Year 1			Year 2				
Activity	Milestones	T1	T2	T3	T4	T1	T2	T3	T4
Data dissemination	Preparing articles for publication								
	Participating in international conferences								
	Developing follow-up studies								
	Developing new preventive strategies								

# Description:

**T1** = September, October, November **T2** = December, January, February

T3 = March, April, May

T4 = June, July, August

# **Dissemination**

To ensure that dissemination is one of the key targets in the project, a specific work package will be developed on dissemination (see WP3: Data dissemination). In this occasion, the objectives, work description and deliverables attached to the dissemination work package will be elaborated, and the variety of communication means and relevant target groups will be taken into consideration.

The objectives for the dissemination of the project are:

- to guarantee that research findings will be communicated to relevant target groups, both in the academic as in the scientific field;
- to develop a dissemination strategy, including dialogue with stakeholders form civic organizations, labour organizations, educational institutions and policy makers in each country.
